Statistical Analysis Plan (Addendum)

An Electronic Brief Alcohol Intervention for Women Attending a Breast Screening Service (Health4Her-Automated)

ClinicalTrials.gov Identifier: [NCT06019442](https://clinicaltrials.gov/ct2/show/study/NCT06019442)

Pre-registered: 31 August 2023

Version: 1

Date version finalised: 7 Feb 2024

Study rationale and design

Alcohol is a major modifiable risk factor for female breast cancer, even in very low amounts. Yet, awareness of this risk remains low and is not systematically addressed in healthcare settings. Embedding a brief alcohol intervention within lifestyle information offered to all women attending breast screening provides the opportunity to address harmful drinking in a discrete, non-judgmental way, to prevent alcohol-attributable breast cancer among this at-risk population.

Building on a previous randomised controlled trial of a prototype brief e-health intervention (which included alcohol-related questions asked by a researcher, and an animation viewed on an iPad that was activated by the researcher), the aim of the current pragmatic, single-site, double-blind, parallel group randomised controlled trial is to test the effectiveness of a co-designed, automated brief alcohol intervention (Health4Her-Automated) in reducing women's drinking intentions, improving alcohol literacy, and reducing consumption.

Women attending Maroondah BreastScreen for routine mammography completed a baseline assessment before being randomised to receive alcohol brief intervention plus lifestyle health promotion, or lifestyle health promotion only. Participants received an iPad and earphones to self-complete interventions. Alcohol and/or lifestyle information was delivered by way of an animation on an iPad, alongside self-completed activities that reinforced intervention content. Follow-up assessments were completed after intervention completion (i.e. immediately post-randomisation; drinking intentions outcome only) and at 4-weeks post-randomisation.

This study also included a pilot arm – active arm but completed post-screening offsite (i.e. at home on own device). The pilot arm did not form part of the planned randomised controlled trial or power and sample size calculation, but was included based on findings from the previous phase of this research (e.g. women not having time to complete the intervention onsite, some breast screening services not having space or resources to deliver the intervention onsite).

Statistical Analysis Plan (SAP)

This plan, or SAP Addendum, provides additional detail to the statistical considerations that were documented in the statistical analysis plan in Health4Her-Automated Protocol_V4_11 08 2023 (available via the [trial record](#) on ClinicalTrials.gov).

Additional analyses not specified in the published protocol or this addendum will be regarded as exploratory.

Statistical software

Analyses will be conducted using the most appropriate procedures in programs such as GenStat, R, SAS, or Stata.

Analytic approach

Data will be collated, cleaned, and validated using programmed edit checks.

The analysis will take place based on the intention to treat (ITT) principle (i.e. subjects' data are analysed as randomised) after all subjects, not known to have withdrawn or not deemed lost to follow-up, have had their 4-week assessments.

Outcome variables with repeated measurements will be analysed by fitting Generalised Linear Mixed Models (GLMMs) with an appropriate link function (e.g. gaussian for continuous outcomes or outcomes treated as continuous [e.g. 5-point Likert scales] and logit for binary outcomes). Inferences about the effect of the Health4Her intervention on the outcomes will be based on a comparison, between treatment groups, of change in outcomes from baseline to immediate post-intervention (i.e. immediately post-randomisation) and/or 4-weeks post-randomisation. Models will estimate fixed effects for treatment and time, and their interaction, and random effects for subjects and assessments within subjects. If necessary, suitable variance-covariance structures for the repeated measures will be compared using Akaike's Information Criterion and/or Bayesian Information Criterion. In the case that GLMMs have estimation/convergence difficulties regression models may be estimated via Generalised Estimating Equations (with an appropriate link function). A Wald test (or equivalent approach) will be used to test for an overall group by time interaction in outcomes.

Outcome variables without a baseline assessment will be examined using Generalised Linear Models (i.e. the non-mixed model version). Inferences about the effect of the Health4Her intervention on these outcomes will be based on a comparison between treatment groups of outcomes assessed at 4-weeks post-randomisation. Models will estimate fixed effects for treatment.

All statistical tests will be two-tailed with the alpha level set to 0.05.

Pilot Arm – active arm but completed post-screening (i.e. offsite on own device)

Inferences about the effect of the Health4Her intervention completed post-screening (i.e. offsite on own device) on outcomes will be based on based on: 1) a comparison of change, in the pilot arm only, from baseline to immediate post-intervention (i.e. immediately post-randomisation) and/or 4-weeks post-randomisation, and 2) a comparison, between treatment groups (i.e. pilot arm vs control; pilot arm vs intervention; acknowledging that assignment to the pilot arm was not randomised), of change from baseline to immediate post-intervention (i.e. immediately post-randomisation) and/or 4-weeks post-randomisation. The analytic methods described above will be implemented here.

Missing data

Where appropriate, missing values will be addressed through maximum likelihood estimation (i.e. in a mixed model) or using multiple imputation.

Sensitivity analyses

Several sensitivity analyses may be performed:

- Using a per-protocol approach, defined as those who received all elements of the intervention.

- Stratified by participants based on those who: a) report drinking any alcohol in the past month, and b) are identified to be drinking at a level exceeding current national guidelines for weekly and/or single day consumption.
- Including relevant covariates (e.g. age, education, CALD, LGBTIQ+A+) as adjustments. Covariates may also be used to stratify analyses.
- Models to examine the robustness of missing data modelling decisions (e.g. including auxiliary variables in models or in complete case data).

Primary Outcome

- 1) Change in next-month drinking intentions (immediate post-intervention)

Secondary Outcomes

- 1) Change in next-month drinking intentions (4-weeks post-randomisation)
- 2) Change in intended number of standard drinks consumed over the next month (4-weeks post-randomisation)
- 3) Proportion of participants intending to reduce their next-month alcohol consumption (immediate post-intervention)
- 4) Proportion of participants intending to reduce their next-month alcohol consumption (4-weeks post-randomisation)
- 5) Proportion of participants accurately identifying alcohol as a clear risk factor for breast cancer (4-weeks post-randomisation)
- 6) Proportion of participants accurately identifying i) the increased breast cancer risk associated with drinking one average restaurant serve of wine a day; ii) the number of standard drinks in an average restaurant serve of red wine; iii) the maximum number of standard drinks per week recommended by current Australian Alcohol Guidelines (4-weeks post-randomisation)
- 7) Proportion of participants accurately identifying inactivity and excess weight as risk factors for breast cancer (4-weeks post-randomisation)
- 8) Proportion of participants sharing the information they learned with others (4-weeks post-randomisation)

Potential additional exploratory outcomes

Potential additional exploratory outcomes include (but are not limited to): change in next-month: physical activity intentions, vegetable consumption intentions; change in: physical activity frequency/amount, vegetable consumption frequency; change in physical activity / diet-related health literacy.

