While this study will examine reach, uptake, feasibility and acceptability as important end-points, it will be powered to test the effectiveness of H4H-A in decreasing women's drinking intentions. The sample size has been calculated using data from a previous, related study examining the effects of alcohol warning information about the alcohol-breast cancer link on drinking intentions (15). Using a Likert 5-point response scale (1 = not at all, 5 = to a very great extent, this study showed that the warning information, *Alcohol increases your risk of breast cancer*, increased participants' intention to reduce the amount of alcohol they consume from a pre-exposure mean of 2.37 (SD = 1.18) to a post-exposure mean of 2.63 (SD = 1.22).

Given some differences in the previous study (i.e. the message about alcohol and breast cancer risk was not personally relevant to the whole sample comprising males and females 18-65 years; a single health message was provided, which is different to the Health4Her intervention containing several 'active ingredients' based on alcohol brief intervention and applied behaviour change principles), we anticipate a greater increase in participants' intention to reduce the amount of alcohol they consume in the current study. Further, based on our previous research, we anticipate some assessment reactivity among the control group.

Power and sample size estimations were conducted using General Linear Mixed Model Power and Sample Size (GLIMPSE) software. We estimate (factoring in 5% attrition, and 30% of women attending breast screening who do not drink or have not drunk in the past month) that a total sample size of at least 78 (39 per group) will have 80% power ($\alpha < 0.05$) (a total sample size of 90 [45 per group] will provide 85% power, $\alpha < 0.05$) to detect a change in women's drinking intentions of 2.37 to 3.37 (change = 1.00) in the intervention group, and a change of 2.37 to 2.63 (change = 0.26) in the control group between baseline and immediately post-intervention. Therefore, this study will aim to recruit a total

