sample size of at least 78 participants. Based on the barriers to participation and implementation identified in the previous phase of this research, the current study will provide an opportunity to collect some pilot data to inform scaled up research and implementation, to provide an indicator of outcomes for participants who complete a modified version of the alcohol brief intervention offsite using their own personal device (n~20).

Statistical analyses: A full Statistical Analyses Plan will be developed prior to trial commencement. All statistical tests will be two-tailed, with the alpha level set to 0.05 and analyses conducted using the most appropriate procedures in Stata or R. All randomised participants will be included in the analyses (i.e. intention-to-treat) for primary and secondary outcomes. Analyses will examine change in outcomes over time (baseline, immediately post-intervention, 4-weeks). For intention outcomes, we will examine differences in responses according to baseline alcohol consumption risk status (i.e. drinking at a level within/exceeding current national alcohol guidelines). For alcohol outcomes, sensitivity analyses will be performed for women who a) report drinking any alcohol in the past month, and b) are identified to be drinking at a level exceeding current national guidelines for weekly and/or single day consumption. The Generalised Linear Mixed Model approach with fixed effects for treatment and time, and their interaction, and random effects for subjects and assessments within subjects, will be applied to examine the treatment effect of the intervention on all outcomes.

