6 STUDY PROCEDURES

6.1 STUDY FLOW CHART

6.2 SCHEDULE OF ASSESSMENTS

| Assessment | Time point: | Pre-trial | Maroondah BreastScreen | | Online survey |
|--|-------------|-----------|-------------------------------------|--------------------------------------|----------------------------------|
| | | | 0 (immediately pre-intervention) | 1 (immediately post-intervention) | 2 (4-weeks post-intervention) |
| COLLABORATIVE DESIGN OF H4H-A | | | | | |
| In-person and online workshops with breast screening service consumers | | x | | | |
| IMPLEMENTATION OF H4H-A^a | | | | | |
| Eligibility assessment (breast screening staff will assess English comprehension; question about access to computer, tablet or | | | x | | |

| | | | | |
|---|--|---|-----------------------------|-------------|
| smartphone embedded at start of intervention) | | | | |
| Trial explanation (embedded at start of intervention) | | x | | |
| PIS (link embedded at start of intervention, and emailed) | | x | | |
| Informed consent (embedded at start of intervention) | | x | | |
| Randomisation | | | x | |
| Intervention | | | x | |
| Measures | | | | |
| Primary outcome | | | | |
| Drinking intentions (5-point Likert scale) | | x | x | x |
| Secondary outcomes | | | | |
| Drinking intentions (QF intentions) | | x | | x |
| Alcohol-breast cancer literacy | | x | | x |
| Alcohol literacy | | x | | x |
| Alcohol consumption (past-month QF) | | x | | x |
| Knowledge of other breast cancer risk factors | | x | | x |
| PROGRAM EVALUATION ^a | | | | |
| Trial / service administrative data collection | | | (throughout implementation) | |
| Participant feedback | | | | (end trial) |
| Site staff and manager feedback | | | | (end trial) |

^a Participants in the modified active arm being piloted will participate in eligibility assessment, informed consent, baseline, intervention, follow-up and program evaluation in the same way as participants in the active / control arms, but will not be randomised and will complete all activities offsite.

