12.2 MODIFICATIONS TO THE PROTOCOL

Protocol amendments will be submitted to the Eastern Health HREC. No changes to the protocol will be implemented without prior approval.

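### The primary model leaves out baseline intention (as a covariate) and baseline drinking status; pre-specifying both would cut the variance of the effect estimate by about 10% to 20% at an inferred pre-post correlation near 0.70

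*SAP*

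**What the plan says.** The SAP, under Analytic approach, rests the primary inference on a between-arm comparison of change in intention score from baseline to immediately post-intervention. It lists the model terms: "Models will estimate fixed effects for treatment and time, and their interaction, and random effects for subjects and assessments within subjects". Protocol section 4.2 (Statistical analyses) specifies a mixed model "with fixed effects for treatment and time, and their interaction", and defines the population: "All randomised participants will be included in the analyses (i.e. intention-to-treat) for primary and secondary outcomes". Women at any level of drinking are eligible, and the sample size paragraph allows for "30% of women attending breast screening who do not drink or have not drunk in the past month".

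The SAP's Sensitivity analyses section, all of it optional, offers stratification by past-month drinking and by guideline excess, and also "Including relevant covariates (e.g. age, education, CALD, LGBTIQ+A+) as adjustments". Protocol section 4.2 says that intention responses will be examined by baseline risk status, and commits to sensitivity analyses in past-month drinkers for alcohol outcomes. None of these provisions changes the primary model.

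The schedule in protocol section 6.2 places the intention item and past-month drinking at the pre-intervention assessment. The SAP confirms the order: "Women attending Maroondah BreastScreen for routine mammography completed a baseline assessment before being randomised".

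**The concern.** With complete data at two time points, the treatment-by-time estimate is the raw difference between arms in mean change. That estimator subtracts the baseline score with a slope of exactly 1. It also lets the arms have different baseline means, although baseline precedes randomisation.

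It further mixes two kinds of women. The primary item asks how far a woman intends to reduce her drinking, and those who do not drink plausibly answer it differently and change less. That variation is predictable from a baseline measure, but the planned model leaves it in the error term.

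The target is 39 per arm, about 37 after 5% attrition, of whom about 26 drink. At this size a wider interval than necessary is a real cost. Leaving adjustment as an optional sensitivity analysis also leaves the choice of covariates open and does not alter the primary estimate or its interval.

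**Working it through.** **Inputs (protocol 4.2, Power and sample size estimate).** Change 1.00 in the intervention arm and 0.26 in control, so the difference is 0.74. SDs 1.18 (pre) and 1.22 (post), from the cited warning-message study. Two-sided alpha 0.05; 39 per arm for 80% power; 5% attrition; 30% non-drinkers. The pre-post correlation r is not stated.

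**Reproducing the plan's figure.** Variance of change = 1.18² + 1.22² − 2r(1.18)(1.22) = 2.8808 − 2.8792r. Solving for 80% power with a noncentral t:

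- both losses applied, 39 × 0.95 × 0.70 ≈ 26 per arm: r = 0.698
- attrition only, 39 × 0.95 ≈ 37 per arm: r = 0.564

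The 85% figure at 45 per arm gives 0.693 with both losses. It uses the same difference and SDs, so it is not independent support.

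**Is the planned contrast raw change?** In a test fit the mixed model and the raw difference in change both gave 0.4917. Adding drinking status as a main effect only still gave 0.4917, because a term that is constant over time drops out of within-woman change.

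**One scenario by hand: r = 0.70, non-drinkers score 1 at both times.**

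- Average effect: 0.70 × 0.74 = 0.518.
- Variance of change among drinkers: 2.8808 − 2.0154 = 0.865.
- Between-group part: 0.21 × (1.00² + 0.26²)/2 = 0.112, where 0.21 = 0.7 × 0.3.
- Total for raw change: 0.7 × 0.865 + 0.112 = 0.718.
- Adjusted for both: drinkers' residual variance is 1.22² × (1 − 0.70²) = 0.759. The part of drinking status not captured by a common shift is 0.21 × 0.37² = 0.029. Total: 0.7 × 0.759 + 0.029 = 0.560.
- Ratio: 0.560/0.718 = 0.78, or about 0.80 after allowing for two extra coefficients in 74 women.

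Baseline score alone does not help in this scenario. The pooled slope is [0.7 × 0.70 × 1.18 × 1.22 + 0.21 × 1.37 × 2.00] / [0.7 × 1.18² + 0.21 × 1.37²] = 1.281/1.369 = 0.94, so the ANCOVA is nearly the change score.

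**Simulation across scenarios** (r = 0.698, 37 per arm, each woman a non-drinker with probability 0.30, normal scores, 40,000 runs per cell). The comparator is the two-time-point change-score test.

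| Non-drinkers | Power, change | Power, baseline only | Power, baseline + drinking | Variance ratio, both vs change | 39/ratio |
|---|---|---|---|---|---|
| Fixed at 1 | 73.8% | 73.3% | 83.2% | 0.802 | 48.6 |
| Start at 1, change SD 0.5 | 69.3% | 68.8% | 78.1% | 0.824 | 47.3 |
| Like untreated controls | 62.6% | 67.3% | 68.9% | 0.877 | 44.5 |
| Half the effect | 80.9% | 85.1% | 85.2% | 0.895 | 43.6 |
| Like drinkers | 92.0% | 94.5% | 94.2% | 0.901 | 43.3 |

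The 95% interval half-width falls from 0.391 to 0.351 (fixed at 1) and from 0.444 to 0.416 (like controls). Mean estimates are essentially the same under all models, and rejection under the null is 4.9% to 5.3%. With scores rounded to 1–5, power rises from 64.3% to 73.5% (fixed at 1), 52.9% to 58.8% (like controls) and 85.5% to 89.0% (like drinkers).

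**Other correlations.** Gain in power over the same five scenarios: 9 to 14 points at 0.5, 6 to 12 at 0.56, 0 to 7 at 0.8, 0 to 4 at 0.9.

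**The case against.** The strongest reply is that nothing here is an error. Difference in change from a treatment-by-time mixed model is a standard analysis. It is stated alike in protocol and SAP, and it matches a hypothesis framed as greater change. That stands: the point is efficiency, not bias.

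Second, the plan already looks at drinkers. Protocol section 4.2 is firmer than the SAP, since it commits to sensitivity analyses in past-month drinkers for alcohol outcomes, and the SAP's covariate list is only illustrative. Whether alcohol outcomes include intentions is unclear, because the protocol treats intentions in a separate sentence. Such analyses can show robustness, but they do not narrow the primary interval.

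Third, the 10% to 20% belongs to one inferred correlation. If non-drinkers respond like drinkers, the variance cut is about 16% at 0.56, 10% at 0.70, 4% at 0.80 and nil at 0.90. If they sit at 1, it is 23%, 20%, 18% and 26%. This is a fair limit, and the figure should always be quoted with its correlation.

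Fourth, 78 is a minimum. With more women the gain in power shrinks: with non-drinkers at 1 and r = 0.70 it is about 10 points at 39 per arm, 5 at 60 and 2 at 80. The proportional cut in variance does not shrink.

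Finally, a pooled random-intercept model over all three assessments could lose further power. That would come from the covariance structure, which the SAP provides for comparing by AIC or BIC. It is a separate matter and is not counted here.

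**Conclusion.** The concern holds as a recommended improvement to a valid analysis. Near r = 0.70, pre-specifying both covariates lowers the variance of the primary estimate by about 10% to 20% and raises power by about 2 to 9 points, using data already scheduled. Drinking status is essential to the proposal: baseline score alone gains nothing if non-drinkers sit at the bottom of the scale.

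Confidence is medium. The result assumes the cited study's SDs, the planning effect of 0.74 in drinkers, 37 evaluable women per arm, and a correlation back-solved on the reading that both losses were applied. If only attrition was applied, the correlation is lower and the gain in power larger. How non-drinkers answer the item is wholly assumed, because the documents give no figures.

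**What to change.** For the two randomised arms, pre-specify as primary an ANCOVA of the immediate post-intervention intention score on arm, baseline intention score and baseline past-month drinking (any versus none). An equivalent mixed model constrains the arms to a common baseline mean and includes drinking status by time. In 1,500 simulated trials its estimates correlated 1.000 with the ANCOVA's, with mean standard errors of 0.174 against 0.176 (fixed at 1) and 0.206 against 0.209 (like controls). Drinking status as a main effect only is not enough. Do not apply the common-baseline constraint to the pilot arm, which is not randomised. Keep the present model as a sensitivity analysis, and state the correlation and SDs used in the sample size calculation.

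The cost is small but not nil. No new data are needed, but both documents must be amended, and protocol section 12.2 says: "No changes to the protocol will be implemented without prior approval". The SAP, dated 7 February 2024, already describes participation in the past tense, so the change needs a dated justification and must precede any look at outcomes by arm. If outcomes have already been examined by arm, leave the primary model as it is and report the adjusted analysis as post hoc.

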3.1 RANDOMISED CONTROLLED TRIAL OUTCOMES/HYPOTHESES

Primary outcome/hypothesis:

- a) *Change in next-month drinking intentions (primary outcome)*: we hypothesise that there will be a greater change in the extent to which participants intend to reduce the amount of alcohol they consume among intervention participants, relative to control, between baseline and immediately post-intervention (likert scale response item) (15).

Secondary outcomes / hypotheses:

- b) *Change in next-month drinking intentions*: we hypothesise that there will be a greater change in the extent to which participants intend to reduce the amount of alcohol they consume

among intervention participants, relative to control, between baseline and 4-weeks post-intervention (likert scale response item) (15).

- c) *Change in drinking intentions – standard drinks*: we hypothesise that there will be a greater reduction in the intended number of standard drinks consumed over the next month among intervention participants, relative to control, between baseline and 4-weeks (quantity/frequency response items) (16).
- d) *Proportion of participants intending to reduce alcohol consumption*: we hypothesise that there will be a greater change in the *proportion* of intervention participants, relative to control, intending to reduce their next-month alcohol consumption between baseline and immediately post-intervention (15).
- e) *Proportion of participants intending to reduce alcohol consumption*: we hypothesise that there will be a greater change in the *proportion* of intervention participants, relative to control, intending to reduce their next-month alcohol consumption between baseline and 4-weeks (15).
- f) *Change in knowledge of alcohol as a breast cancer risk factor (alcohol-breast cancer literacy)*: we hypothesise that there will be a greater change in the proportion of intervention participants accurately identifying alcohol as a risk factor for breast cancer between baseline and 4-weeks, compared to control participants.

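### For the repeated yes/no outcomes, the stated random effect for each assessment is not identifiable in practice, so the size of the conditional odds ratio is left almost undetermined

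*SAP*

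**What the plan says.** The SAP (Analytic approach) plans generalised linear mixed models for all outcomes measured more than once, with a Gaussian model for continuous or Likert outcomes and "logit for binary outcomes". One structure then serves both: fixed effects for treatment, time and their interaction, and "random effects for subjects and assessments within subjects". Section 4.2 of the protocol repeats this: "random effects for subjects and assessments within subjects, will be applied to examine the treatment effect of the intervention on all outcomes". Neither document exempts the binary outcomes.

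The schedule in protocol section 6.2 has each measure taken once per visit. The literacy row reads "Alcohol literacy | | x | | x" (baseline and 4 weeks) and the intention row reads "Drinking intentions (5-point Likert scale) | | x | x | x" (all three time points).

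The SAP adds three relevant provisions:
- Covariance structures may be compared by AIC or BIC, if necessary.
- If the mixed model has estimation or convergence difficulties, "regression models may be estimated via Generalised Estimating Equations".
- The group-by-time interaction is tested by a Wald or equivalent test.

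Outcomes with no baseline go to an ordinary generalised linear model. The pilot-arm comparisons use the same methods. The hypotheses in protocol section 3.1 concern proportions, for example "we hypothesise that there will be a greater change in the proportion of intervention participants accurately identifying alcohol as a risk factor".

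**The concern.** In a Gaussian model with one value per visit, a random effect for assessment within subject is the residual, so naming it does no harm. In a logit model for a single 0/1 value there is no residual variance to estimate, because the Bernoulli distribution fixes it. An added assessment-level effect is then a further latent variance on one yes/no answer. Raising it stretches the logit scale: the subject variance and the regression coefficients grow to compensate, and the fitted proportions stay where they were.

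Secondary outcomes 3 to 7 in the SAP all go through this model: intending to reduce drinking (two time points), alcohol as a risk factor, the three literacy items, and inactivity and excess weight. If the text is followed literally, the size of each conditional odds ratio, and its upper confidence limit, depend on where the optimiser stops. If GEE is used for some outcomes, their odds ratios are population-averaged, and the plan does not say which kind is wanted.

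**Working it through.** **The plan's own figure.** There is none to reproduce. The documents give no effect size, power or target odds ratio for the binary outcomes. The 78 women for 80% power relate to the Likert primary outcome, and only the 39 per arm is used here.

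**Inputs.**
- 39 per arm: protocol section 4.2.
- Baseline knowledge about 20%: protocol section 2 reports that four in five lacked it in the previous trial.
- Proportions at 4 weeks of 40% (control) and 70% (intervention), and a between-woman SD of 1.5 on the logit scale: assumptions.

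**Model.** logit P(yes) = (arm-by-visit mean) + u + e, with u ~ N(0, σ_u²) for the woman and e ~ N(0, σ_e²) for the assessment. Expected two-visit cell counts were generated with σ_e² = 0. Then σ_e² was fixed at several values and all other parameters were re-estimated by maximum likelihood with numerical quadrature.

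| σ_e² fixed at | −log-likelihood | Conditional arm-by-time OR |
|---|---|---|
| 0 | 86.9948 | 5.8 |
| 1 | 86.9950 | 7.8 |
| 4 | 86.9955 | 15.4 |
| 9 | 86.9957 | 35.6 |
| 25 | 86.9958 | 230 |

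The log-likelihood changes by 86.9958 − 86.9948 = 0.0010, a deviance change of 0.002, against the 3.84 needed to reject at 5%. The fitted proportions stay at 20%, 40% and 70%, so the difference in change is (70 − 20) − (40 − 20) = 30 percentage points in every row.

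**Effect on the test and the interval.** The Wald z for the interaction goes from 1.87 to 1.93.
- σ_e² = 0: ln 5.81 = 1.760, SE = 1.760/1.87 = 0.941, 95% limits exp(1.760 ± 1.96 × 0.941) = 0.92 to about 37.
- σ_e² = 25: ln 230 = 5.438, SE = 5.438/1.93 = 2.818, limits exp(5.438 ± 1.96 × 2.818) = 0.92 to roughly 57,000.

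The lower limit and the test are stable. The point estimate and upper limit are not.

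**Marginal odds ratio.** The arms have the same baseline odds, so these cancel: (0.7/0.3)/(0.4/0.6) = 3.5, against 5.8 for the conditional odds ratio with no assessment effect.

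**Other inputs.**
- The previous trial's within-arm odds ratios (41.82 and 4.92, protocol section 2) were treated, as an assumption, as subject-specific, with subject SD 1.5 and baseline 20%. With no assessment effect the interaction odds ratio is 41.82/4.92 = 8.5. It rises to 2277 at an assessment SD of 6. The deviance rises by at most 0.005, or at most 0.12 with 1000 per arm, so a larger sample does not cure the problem. Wald z runs from 2.14 to 2.23. The marginal odds ratio is 4.66.
- A three-visit yes/no intention outcome was given an assumed 40% baseline, subject SD 2, and logit shifts of 0.4 in control at both later visits and 1.6 then 1.2 in the intervention arm. Over assessment SDs 0 to 6 the odds ratio runs from 3.3 to 80 immediately post-intervention and from 2.2 to 18.6 at 4 weeks. The deviance rises by at most 0.0012, and the 4-week z is 0.95 throughout. The marginal odds ratios are 2.07 and 1.62.

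**The case against.** **The phrase may not mean an added latent effect.** One generic sentence covers Gaussian and logit models, and the next speaks of covariance structures for the repeated measures, so the authors may have meant the within-woman covariance. That is possible. But the text says random effects, and nothing settles the point for binary outcomes, which is itself a reason to clarify.

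**AIC or BIC would drop the term.** If models with and without it were compared, this is right: a deviance change of 0.002 cannot offset an AIC penalty of 2. In 150 datasets simulated from the first scenario, AIC never preferred the extra term. The SAP makes the comparison only if necessary, however, so it is not a dependable safeguard.

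**Inference is barely touched.** This stands. The planned inference is the Wald interaction test, and z hardly changes.

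**No odds ratio is named as the reported effect.** This also stands. The documents report odds ratios only for the previous trial. Still, a logit mixed model yields one, and the plan names no other effect measure.

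A reader might infer that the term will make the models fail and so switch the analysis to GEE. The documents do not support that. GEE is permitted, not required, and failure has not been shown: in the same 150 datasets a bounded optimiser reported convergence every time. In at least a quarter, though, the variance ran to its bound and the odds ratio was hugely inflated. The more likely trouble is a converged but arbitrary estimate. Packages may differ, and software settings were not varied here.

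**Conclusion.** The point holds for the repeated binary outcomes, secondary 3 to 7, and for the same outcomes in the pilot-arm comparisons. Taken literally, the plan leaves the conditional odds ratio essentially undetermined: 5.8 to 230 in the illustration for a log-likelihood change of 0.001. Those sizes rest on the assumed 40%, 70% and subject SD of 1.5. The flat likelihood itself recurred under the other inputs tried.

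Three stronger readings are not supported:
- Strict non-identifiability is too much. With a logit link the shape of the curve carries a trace of information, so the variance is weakly identified.
- The hypothesis tests are not invalidated, since z moves only from 1.87 to 1.93 (2.14 to 2.23 with the other two-visit inputs).
- The trial's main result is not at risk. The primary Likert outcome is Gaussian, where the term is the residual, and information sharing has no baseline and uses an ordinary generalised linear model.

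Separately, the conditional and GEE odds ratios are different quantities (5.8 and 3.5 here), and the plan does not say which it targets.

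**What to change.** In the SAP (Analytic approach), add that for binary outcomes with repeated measurements the random part of the model is *a random intercept for subject only*. Protocol section 4.2 should be read, or amended, to match. Add that any odds ratio will be labelled conditional if it comes from the mixed model and marginal if it comes from GEE.

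Optionally, under either method, also report model-standardised proportions by arm and visit, with the between-arm difference in change and its 95% CI. These are comparable across mixed model and GEE and speak directly to hypotheses about proportions. This is a choice of presentation, not part of the correction.

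The correction costs a few words and no new data. The optional step needs a little post-estimation programming, and an interval on the difference scale may not agree exactly with the Wald test on the logit scale. The SAP should therefore say that the Wald test remains the planned test.
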